4.3 PRIMARY ENDPOINT(S) ANALYSIS

4.3.1 Definition of endpoint(s)

The primary endpoint is the difference from baseline to week 16 in the percentage of TIR of 70-180 mg/dL using 14 days of CGM data at baseline. The percentage of time spent in the glycemic target range will be calculated as 100 times the number of recorded measurements in the glycemic target range, (70-180 mg/dL) inclusive, divided by the total number of recorded measurements. All the efficacy assessments collected during the study will be used, including those obtained after IMP discontinuation or introduction of rescue therapy. Regardless of intercurrent events at week 16, the value for the mean change in the percentage of TIR will be used.

CGM data

CGM compliance is defined as:

1. at least 8 out of 14 days (not necessarily consecutive) have 100% of evaluable CGM data per 24-hour period (total of 768 records on 8 days) OR
2. at least 9 out of 14 days (not necessarily consecutive) have $\geq 89\%$ of evaluable CGM data per 24-hour period (total of 768 records on 9 days and at least 9 days with 85 records minimum) OR
3. at least 10 out of 14 days (not necessarily consecutive) have at least $\geq 80\%$ of evaluable CGM data per 24-hour period (total of 768 records on 10 days and at least 10 days with 77 records minimum)

during baseline (the run-in period) as well as week 16.

During the run-in period or end of treatment period, CGM device reinsertion will be allowed for participants who do not meet the compliance criteria over a 14-day period as a result of premature sensor failure.

Baseline will be defined as the first 14 evaluable days of evaluable CGM data prior to first day of treatment and referred to as the run-in period in the graphical study design. An evaluable day is defined as a 24-hour period with $\geq 80\%$ non-missing measurements. Only evaluable days will be included in the analysis. Week 16 will be defined as the first 14 evaluable days of evaluable CGM data starting at day 95 or later.

The first day of CGM data will start at time of device insertion and subsequent days will start every 24 hours. If the device is re-inserted, device with the most compliant data will be used and if neither session is evaluable, the combined data from both sessions will be used as evaluable data. For subsequent reinsertions, the day will start at time of reinsertion.

Unless otherwise specified, outcome variables based on CGM data will use subjects in the efficacy analysis set with compliant data at baseline.

Percent time in the glucose range is defined as the total number of 15-minute increments where a participant's blood glucose falls within range of ≥ 70 to ≤ 180 mg/dL (≥ 3.9 to ≤ 10 mmol/L) divided by the total number of observed 15-minute increments in that period. Percent time in range will be calculated for baseline (run-in) and for week 16.

4.3.2 Main analytical approach

Mean change (in percentage) from baseline and its associated 95% CI will be calculated using subjects in the efficacy analysis set with compliant baseline CGM data. A one-sample t-test will be applied to test the significance of changes at week 16 over baseline (run-in). The statistical test will be a 2-sided at a nominal 5% significance level.

Hypothesis Testing of the Primary Endpoint

H0: There is no improvement in TIR at week 16 compared with baseline.

H1: There is an increase in TIR at week 16 compared with baseline.

A two-sided 95% CI will be presented, superiority versus baseline will be demonstrated if the lower bound is above 0.

Missing data will be handled differently in accordance with the reasons for missing data. If the missing data are due to technical issues with the CGM device (ie, CGM data are not evaluable as per the CGM compliance rule [Section 4.3.1](#) during the 2-week run-in period [baseline] as well as the end of the treatment period [ie, from Weeks 14 to 16], the participant will be excluded from the analysis (missing completely at random [MCAR] approach). For all other reasons the Week 16 assessment will be imputed with the baseline observation carried forward (BOCF); therefore, change from baseline will be 0.

The MCAR assumption will be non-conclusively evaluated by testing the association between the baseline covariates and missing data status at Week 16. Specifically, a contingency table will be constructed based on the missing data status at Week 16 and a given categorical baseline covariate. If all the expected cell counts exceed 5, the association will be tested by chi-square test; otherwise, Fisher's exact test will be used.

4.3.3 Sensitivity analyses

As a sensitivity analysis, the primary analysis will be repeated to include participants with any missing data due to discontinuation or non-compliant data at Week 16 by imputing with BOCF. The mean and its associated 95% CI will be reported.

As a second sensitivity analysis, the primary analysis will be repeated for all participants in the efficacy analysis set. All missing data at Baseline and Week 16 will be excluded and not imputed, and only compliant CGM data will be utilized. Mean and its associated 95% CI will be reported.

4.3.4 Supplementary analyses

No analysis is planned.

4.3.5 Subgroup analyses

The primary analysis will be replicated, if the number of participants in a specific subgroup is at least 20, for the following subgroups:

- Participants using OAD only at baseline
- Participants using OAD plus GLP-1RA at baseline
- Participants ≥ 65 years of age
- Participants < 65 years of age.

In these subgroup analyses, mean (SD) and associated 95% CI, as well as minimum, median, and maximum will be provided.

4.4 SECONDARY ENDPOINT(S) ANALYSIS

4.4.1 Key/Confirmatory secondary endpoint(s)

4.4.1.1 Definition of endpoint(s)

Key Secondary Endpoints:

- Change (%) from baseline (run-in) to week 16 in glucose total CV. The data for this endpoint come from the CGM data using the glucose readings. The endpoint will be calculated globally (percent change from the total two weeks baseline CV to the two weeks end of treatment week 16 CV). The CV formula used is $CV\%_{total} = \frac{SD_{total}}{\bar{x}} * 100\%$ where $SD_{total} = \sqrt{\frac{\sum(x_i - \bar{x})^2}{n-1}}$, x_i is the individual glucose reading value, \bar{x} is the 14-day mean and n is the number of data points and the % change will be reported. The alternative hypothesis to be tested is that the CV differs between baseline and week 16. A two-sided 95% CI will be presented.
- Change (mg/dL) from baseline (run-in) to week 16 in mean daily blood glucose. These data come from the CGM data and will be calculated for each day by using the average blood glucose for week 16 compared to the parallel day during the run-in period (baseline) [for example, Day 1 of baseline's average blood glucose will be compared to Day 1 of week 16's average blood]. A global average will be computed to determine the average of the mean daily blood glucose for the 14 days at baseline and also at week 16. The global average will be used for hierarchical testing and the mg/dL change will be reported. The alternative hypotheses to be tested is that mean daily blood glucose differs between baseline and week 16. Two-sided 95% CIs will be presented.
- Change (mg/dL) from baseline (run-in) to week 16 in the maximum PPG exposure in the 4 hours after the breakfast meal during the mixed-meal tolerance test collected from the CRF. The analysis is focused on the 4-hour interval at both baseline (run-in) and week 16 from t=0 (the timepoint at which glucose measurement is taken immediately preceding meal administration) throughout the subsequent 4 hours. For each participant, the overall maximum glucose value (mg/dL) within the described 4-hour period will be determined, and the difference between the maximum glucose value at baseline(run-in) and week 16 will be reported. The alternative hypothesis to be tested is that the maximum PPG differ between baseline and week 16. A two-sided 95% CI will be presented. This analysis will be based on participants in the enrolled set who have non-missing outcomes at baseline.
- Change (%) from baseline (run-in) to week 16 in TAR (>180 mg/dL). The percentage of time spent above the glycemic target range will be calculated as 100 times the total number of 15-minute increments of CGM data where a participant's blood glucose falls above normal range (>180 mg/dL) in a 14-day period divided by the total number of 15-minute increments read (up to 1344 15-minute increments). This will be calculated for

baseline (run-in) and for week 16 and the change will be reported. The alternative hypothesis to be tested is that the TAR differs between baseline and week 16. A two-sided 95% CI will be presented.

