6.2.2 MMTT-Derived β-Cell Function and PPG Measures

Participants will undergo the MMTT (while wearing the CGM device) to assess maximum PPG exposure in the 4-hour period after the breakfast meal (tested at a central laboratory) with biomarkers of β -cell function (plasma glucose, insulin, and C-peptide) measured at Visit 3.1 (ie, site visit during the baseline period). The baseline MMTT will be conducted before discontinuing the daily (oral or injectable) or weekly GLP-1 RA, DPP-4i, or down-titration of SU by 50%. At Visit 3.1, participants on OADs or an oral or injectable GLP-1 RA will be required to take their dose after the blood sample for FPG and HbA1c is collected and 30 minutes before administration of the meal during the MMTT. Participants on weekly GLP-1 RA should have their baseline MMTT conducted within 7 (\pm 3) days after their last dose. During baseline (Visit 3.1), blood samples will be collected at the following time points: premeal (30 min) and just before administration of OADs or GLP-1 RA (oral or injectable) (baseline); time 0 (just before meal administration), 10 min, 20 min; and 0.5, 1.0, 1.5, 2.0, 2.5, 3.0, and 4.0 hours post-meal for plasma glucose, C-peptide, and insulin levels.

At the end of the treatment period (Visit 7), participants will again undergo the MMTT (while wearing the CGM device; only to derive PPG measures). Soliqua 100/33 should be administered 30 minutes before administration of the meal during the MMTT at Visit 7. At the end of the treatment period (Visit 7), blood samples will be collected for plasma glucose levels, as follows: premeal (30 min) and just before administration of Soliqua 100/33; and time 0 (just before meal administration), 0.5, 1.0, 1.5, 2.0, 2.5, 3.0, and 4.0 hours post-meal. These values will be used for PPG analyses with the goal of deriving reduction in the maximum glucose exposure in the 4-hour period after the breakfast meal following Soliqua 100/33 administration at Week 16 compared with baseline. During both baseline and end-of-treatment assessments, removal of the CGM device and download of data will be done after completion of the MMTT (Section 13.1).

The MMTT includes a standardized meal (ie, Boost Very High Calorie) that contains approximately 530 kcal and is composed of 19% carbohydrates, 44% protein, and 33% fat. The composition and the quantity of the standardized meal must be identical throughout the study period.

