8.7 Statistical Analysis Methodology

Statistical analysis will be performed using SAS Enterprise software Version 7.1 or higher. In general, descriptive statistics of quantitative efficacy and safety parameters (result and change from baseline) by scheduled visits will be provided on observed cases (OC; ie, inclusion of only participants having non-missing assessments at a specific visit). The baseline value is defined as the last available value before the first injection of Soliqua 100/33. All efficacy analyses (primary, key secondary, secondary, and other efficacy endpoints) will be performed on the efficacy analysis set. Analysis of demographics, baseline characteristics, and prior and concomitant medications will be provided in detail in the SAP. The extent of study treatment exposure and adherence will be assessed and summarized with dose frequency and duration of treatment.

Continuous data will be summarized using number of observations available, mean, SD, minimum, median, and maximum. Categorical data will be summarized using count and percentage.

Details of the statistical analyses, methods, and data conventions are described in the SAP.

All statistical tests will be 2-sided and performed using a 0.05 significance level, leading to 95% (2-sided) confidence intervals (CIs).

Laboratory values below the lower limit of quantification (LLOQ) will be set to ½LLOQ.

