- Change from baseline (run-in) to week 16 in the 4-hour PPG area under the concentration time curve from 0 to 4 hours (AUC_{0-4h}) after start of the breakfast meal, including determination of the time to reach maximum associated concentration (T_{max}), are both based on MMTT data. T_{max} will be calculated by finding the time that corresponds to the maximum glucose concentration from $t=0$ over the 4 hrs. The 4 hour PPG AUC will be calculated from the glucose values measured at time 0 (just before the meal), 0.5 hours, 1.0 hours, 1.5 hours, 2.0 hours, 2.5 hours, 3.0 hours, and 4.0 hours post-meal utilizing the “trapezoidal rule” $AUC = \sum_{i=0}^{4 \text{ hr}} \frac{[C_{gluc(i+1)} + C_{gluc(i)}]}{2} (t_{i+1} - t_i)$ where C=concentration, i = specified time intervals in the MMTT, and t =time. Differences in (AUC_{0-4h}) from baseline (run-in) to week 16 will be reported as well as the corresponding T_{max} at baseline and week 16. Two-sided 95% CIs will be presented. This analysis will be based on participants in the enrolled set who have non-missing outcomes at baseline and week 16.
- Proportion (%) of participants at week 16 who spend < 15 minutes/day at a glucose level <54 mg/dL. The endpoint will be summarized based upon CGM data reporting both percentages and 95% CI using the Clopper Pearson exact method. A two-sided 95% CI will be presented.

Measures of glycemic control and variability will be presented at baseline and at the end of the treatment period (Week 16). The mean (SD) and associated 95% CI, as well as minimum, median, and maximum values will be provided.

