- p The MMTT includes a standardized meal (ie, Boost Very High Calorie) that contains approximately 530 kcal and is composed of 19% carbohydrates, 44% protein, and 33% fat. The composition and the quantity of the standardized meal must be identical throughout the study period. Baseline MMTT is to be performed before discontinuation of daily (oral or injectable) or weekly GLP-1RA, DPP-4i, or down-titration of SU medications. Participants on weekly GLP-1RA should have their baseline MMTT conducted within 7 (\pm 3) days after their last dose. During the baseline (Visit 3.1), blood samples will be collected at the following time points: premeal (30 min) and just before administration of OADs or GLP-1RA (oral or injectable) (baseline); time 0 (just before meal administration); 10 min; 20 min; and 0.5, 1.0, 1.5, 2.0, 2.5, 3.0, and 4.0 hours post-meal for plasma glucose, C-peptide, and insulin levels. At Visit 3.1, participants on OADs or an oral or injectable GLP-1RA will be required to take their dose after blood sample for FPG and HbA1c is collected and 30 minutes before administration of the meal during the MMTT (during which measures for both β -cell function and PPG analyses will be captured). Soliqua 100/33 should be administered 30 minutes before administration of the meal during the MMTT at Visit 7 (during which only measures for PPG analyses will be captured). At the end of the treatment period (Visit 7), blood samples will be collected for plasma glucose levels, as follows: premeal (30 min) and just before administration of Soliqua 100/33; and time 0 (just before meal administration); 0.5, 1.0, 1.5, 2.0, 2.5, 3.0, and 4.0 hours post-meal. These values will be used for PPG analyses with the goal of deriving reduction in maximum glucose exposure in the 4-hour period after the breakfast meal after Soliqua 100/33 administration at Week 16 compared with baseline.
- q At baseline, the CGM device will be removed and the data will be downloaded on Day -1 at their next site visit (ie, Visit 3.1), after collection of C-peptide, insulin, and plasma glucose data from the MMTT. Downloaded CGM data will be reviewed by the investigator to determine participants' study eligibility. At the end of the treatment period, the CGM device will be removed and the

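### Maximum PPG and Tmax draw on 10 glucose samples at baseline but 8 at Week 16, which tilts the maximum towards a reduction

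*SAP*

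**What the plan says.** Protocol 6.2.2 gives the plasma glucose times for the mixed-meal test. At Visit 3.1 (baseline) they are "time 0 (just before meal administration), 10 min, 20 min; and 0.5, 1.0, 1.5, 2.0, 2.5, 3.0, and 4.0 hours post-meal". At Visit 7 (Week 16) they are "time 0 (just before meal administration), 0.5, 1.0, 1.5, 2.0, 2.5, 3.0, and 4.0 hours post-meal". Each visit also has a sample 30 minutes before the meal, which lies outside the 0 to 4 hour window. The SAP repeats the baseline list in its schedule of events (5.4.5): "time 0 (just before meal administration); 10 min; 20 min; and 0.5, 1.0, 1.5, 2.0, 2.5, 3.0, and 4.0 hours post-meal for plasma glucose".

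For the key secondary endpoint, SAP 4.4.1.1 states: "The analysis is focused on the 4-hour interval at both baseline (run-in) and week 16". Within that interval "the overall maximum glucose value (mg/dL) within the described 4-hour period will be determined", and the difference between visits is analysed. No sample times are listed. In SAP 4.4.2, Tmax "will be calculated by finding the time that corresponds to the maximum glucose concentration", counted from time 0 over 4 hours and again with no list. The AUC in the same bullet does have one: "The 4 hour PPG AUC will be calculated from the glucose values measured at time 0 (just before the meal), 0.5 hours, 1.0 hours", continuing to 4.0 hours through the eight times that both visits share.

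SAP 4.6 places maximum PPG third of four key secondary endpoints in a fixed testing order, ahead of TAR above 180 mg/dL.

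**The concern.** The endpoint compares the highest of ten readings with the highest of eight. The two additional baseline readings can raise the baseline maximum and can never lower it. If the drug did nothing, the expected change from baseline would still be zero or negative, which is the direction of benefit. In a single-arm before-and-after study, a measurement difference between visits goes straight into the estimated effect.

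Maximum PPG is formally tested, and significance there opens the test of TAR. Tmax is only supportive, but its comparison is also unequal: baseline can return 10 or 20 minutes, whereas the earliest post-meal time that Week 16 can return is 30 minutes. An earlier baseline Tmax would look like a later peak on treatment.

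**Working it through.** **Figures in the plan.** The documents give no effect size, SD or power for maximum PPG or Tmax. Their only size calculation is for TIR and is not in dispute: with n = 82, difference 10 and SD 25, the noncentrality is 10/(25/√82) = 3.62, which gives 94.7% power by the t distribution (95.2% by the normal approximation) against the stated 95%.

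**Sample count in the 0 to 4 hour window (Protocol 6.2.2)**
- Baseline: 0, 10, 20, 30, 60, 90, 120, 150, 180, 240 min = 10 samples.
- Week 16: 0, 30, 60, 90, 120, 150, 180, 240 min = 8 samples.
- Only at baseline: 10 and 20 min.

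**Direction.** The eight times are a subset of the ten, so max(10) ≥ max(8) for every participant. With identical true curves at both visits, E[Week 16 − baseline] ≤ 0, and it is strictly negative whenever a baseline maximum can fall at 10 or 20 min. This needs no assumption about the curve.

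**Size (assumed inputs).** Each scenario simulates 400,000 participants whose true curve is the same at both visits:
- glucose = 200 + A·[(t/p)·exp(1 − t/p)]² plus independent noise;
- mean excursion A of 20 or 100 mg/dL (between-participant SD 30% of the mean);
- noise SD of 3, 8 or 15 mg/dL;
- peak time p varying between participants.

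Type I error is for the two-sided 0.05 t-test with n = 85 (100 enrolled × 0.85) and an assumed SD of change of 50 mg/dL, so the noncentrality is bias/(50/√85) = bias/5.42. For example, 1.68/5.42 = 0.31 gives 0.061.

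| Mean peak (SD), min | Baseline maxima at 10 or 20 min | Bias in change, mg/dL | Baseline Tmax earlier by, min | Type I error |
|---|---|---|---|---|
| 120 (30) | 0.1 to 6.1% | −0.01 to −0.4 | 0.02 to 6.2 | 0.050 to 0.051 |
| 90 (30) | 1.5 to 9.4% | −0.1 to −0.8 | 0.2 to 8.0 | 0.050 to 0.052 |
| 60 (20) | 4.0 to 15.5% | −0.3 to −1.7 | 0.5 to 11.3 | 0.050 to 0.061 |
| 40 (15) | 15.7 to 26.8% | −1.3 to −6.2 | 2.1 to 18.0 | 0.056 to 0.205 |
| 25 (8) | 40.9 to 52.8% | −3.2 to −16.0 | 5.9 to 28.2 | 0.09 to 0.83 |

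**Limiting case for Tmax.** With no meal response and equal independent noise, every sample is equally likely to be the maximum. Mean Tmax is then the mean sample time: 900/10 = 90 min at baseline and 870/8 = 108.75 min at Week 16, an apparent delay of 18.75 min from sampling alone.

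**With the eight shared times at both visits,** the comparison is 8 with 8 and the bias from unequal sampling is exactly 0 for both measures.

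**The case against.** *The SAP does not say that all samples are used.* It is silent, and the eight-time list sits in the same bullet as Tmax, so an analyst might apply it to both. The two early draws could also be seen as belonging to the beta-cell panel, which is taken only at baseline. This stands in part: the all-samples reading is natural but not forced. However, the list is attached to the AUC sentence and does not appear in 4.4.1.1. Nothing reserves the early glucose values for beta-cell work, and Protocol 3.1 says the Visit 3.1 meal test serves both beta-cell and PPG analyses. A programmer following the text would include them.

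*The size is assumed and probably small.* This stands. If every participant peaks at the same time, 1.0 to 1.25 h, with an excursion of 60 to 90 mg/dL, the bias is only 0.0 to 0.6 mg/dL and the Tmax shift 0 to 4 min. Much depends on how peak times vary: for a mean of 60 min, the same excursions and noise SD of 8 to 12 mg/dL, a between-participant SD of 20 min brings the bias to about 0.7 to 1.4 mg/dL. The documents give no support for peaks as early as 25 to 40 min, where the large distortions arise. Participants whose Week 16 meal test is imputed by BOCF (SAP 4.4.1.2) contribute zero change and dilute the bias further.

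*Tmax is not in the testing hierarchy.* Correct. For Tmax the matter is one of interpretation, not of type I error.

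**Conclusion.** The point holds. The counts (10 against 8) and the direction for the maximum follow from the documents alone. The size does not: on assumed curves the bias is below about 2 mg/dL for mean peaks at 60 minutes or later, with type I error no higher than about 0.061 at n = 85 and an SD of change of 50 mg/dL. It becomes material only for earlier peaks. It is unlikely to matter against a large drug effect. The change should still be made, because the bias favours the drug on a gatekept endpoint, no control arm offsets it, and the SAP already applies the remedy to the AUC.

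**What to change.** In SAP 4.4.1.1 and 4.4.2, state that maximum PPG and Tmax at both visits are derived only from the samples at 0, 0.5, 1.0, 1.5, 2.0, 2.5, 3.0 and 4.0 hours, as for the AUC. If wanted, report the ten-sample baseline maximum as a sensitivity analysis. The cost is one sentence in the SAP before database lock. Data collection, sample size and alpha do not change, and the 10- and 20-minute samples remain available for the beta-cell modelling.

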4.4.1.2 Main analytical approach

The key secondary estimand will be estimated based on the efficacy analysis set using measurements obtained during the study, regardless of intercurrent events. All four endpoints are continuous and will be summarized using the number of observations available, mean, SD, minimum, median, and maximum. Mean changes for continuous outcomes will be presented at baseline and at the end of the treatment period (Week 16). Mean (SD) and associated 95% CI, as well as minimum, median, and maximum values will be provided, and the analysis will be tested with 2-sided tests at 5% significance level.

Key Secondary endpoints will undergo hierarchical testing in the order displayed in [Section 4.6](#), using two-sample t-test. The results of the test will be displayed in a summary table.

Missing data handling of key CGM secondary endpoints will follow the same approach as the primary estimand.

Regarding participants who discontinue treatment early, but complete the early termination visit per protocol and have MMTT collected at the EOT visit, their data will be used if collected on study day 56 or later; otherwise, the week 16 outcome will be imputed. If the week 16 MMTT data were collected prior to day 56 or missed, then the week 16 outcome will be imputed using baseline observation carried forward (BOCF).

